---

## A Introduction

### A1 Study Abstract

This is a randomized controlled trial examining the effects of one experimental factor (combination Nicotine Replacement Therapy (NRT) vs. varenicline vs. placebo for 3 months) and one non-experimental participant characteristic: CHRNA5 genotypes associated with high, intermediate, and low risk levels for nicotine dependence and smoking cessation failure. Based on the frequency distribution of these genotypes, there will be sufficient numbers of each genetic group represented in the active and placebo arm. All patients will receive intensive smoking cessation counseling. We will examine the main effects of medication (combination NRT vs. varenicline vs. placebo) and genotype (high, intermediate, and low risk), as well as the pharmacogenetic interaction between genotype and medication on the primary cessation outcome (abstinence at end of treatment, ABST\_EOT) and other outcomes (abstinence at 6 months). We chose the primary efficacy measure of abstinence at 3 months (EOT) because preliminary data (Chen et al., 2012) suggest the genetic effects on cessation take place in the early cessation stage. Our hypothesis is that NRT significantly increases smoking abstinence in patients possessing high-risk haplotypes, but not amongst patients without such haplotypes.

This experiment will answer the following questions:

- 1) Is there a genotype X Pharmacotherapy (cNRT vs. placebo) interaction with regard to abstinence?
- 2) Is there a genotype X Pharmacotherapy (varenicline vs. placebo) interaction with regard to abstinence?

This study has been designed following the guidelines and recommendations for conducting and reporting the results of clinical trials as described in the CONSORT (Consolidated Standards of Reporting Trials) statement. In addition, the design and methodology of the study are consistent with current guidelines and recommendations provided by the clinical trial experts in smoking cessation (Society for Research on Nicotine and Tobacco recommendations for follow-up procedures).

### A2 Primary Hypothesis

Hypothesis #1 is to examine whether medication effect (cNRT vs. placebo) varies with CHRNA5 (i.e. a genotype X medication interaction). A series of logistic regression models will be used to examine main effects of genotype (rs16969968) and medication before testing genotype x medication interactions, with sex, age, and study cohort as covariates using logistic regression models.

Hypothesis #2 is to examine whether medication effect (varenicline vs. placebo) varies with CHRNA5 (i.e. a genotype X medication interaction). A series of logistic regression models will be used to examine main effects of genotype (rs16969968) and medication before testing genotype x medication interactions, with sex, age, and study cohort as covariates using logistic regression models.

### **A3 Purpose of the Study Protocol**

This experiment will answer the following questions:

- 1) Is there a genotype X Pharmacotherapy (cNRT vs. placebo) interaction with regard to abstinence?
- 2) Is there a genotype X Pharmacotherapy (varenicline vs. placebo) interaction with regard to abstinence?

## **B Background**

### **B1 Prior Literature and Studies**

In a general population sample of smokers seeking to quit, we recently discovered that genetic markers in the *CHRNA5* gene predict cessation success and response to pharmacotherapy. Patients with the high-risk variants had a 3-fold enhanced response to pharmacotherapy as compared to those with the low-risk and intermediate-risk variants. This information can be used to separate patients who are at serious risk of smoking relapse without pharmacotherapy from those who are likely to be able to quit on their own and thus not benefit from the medication (Chen et al, 2012). These results have been replicated in the large Pharmacogenetics of Nicotine Addiction Treatment (PNAT) consortium (Bergen et al, 2012). To address the current barriers to pharmacotherapy use which lead to failed smoking cessation in these patients, this genetically informed treatment study will investigate how genetic information can be used to personalize cessation pharmacotherapy to maximize efficacy for patients.

### **B2 Rationale for this Study**

Our overarching goal is to identify the most appropriate genetically informed smoking cessation treatments for smokers hoping to quit.

Our recent finding suggests that the effect of pharmacotherapy on cessation varies with genotype (nicotinic receptor gene, *CHRNA5*): pharmacotherapy significantly increases abstinence amongst individuals with the high-risk genetic variants, but provides little benefit to individuals with the low-risk variants. The genotype is useful to predict relapses and response to medication (Chen et al, 2012). Weighing both risk and efficacy on cessation success we will identify smokers who are more likely to relapse, and need pharmacotherapy in order to attain optimal outcomes versus those who will receive little benefit from pharmacotherapy. This work can lead to personalized treatment that promotes long term cessation success by focusing pharmacotherapy use on those who can benefit from it.

## **C Study Objectives**

### **C1 Primary Aim**

Specific Aim 1: To recruit 822 participants who are active smokers in a smoking cessation trial. All patients will be randomized to combination NRT (Nicotine Replacement Therapy) with nicotine patch and lozenge, or varenicline, or placebo for 3 months. All patients will receive intensive smoking counseling. These patients will be assessed in person at baseline, 3 months (if biochemical verification of abstinence is needed), 6 months (if biochemical verification of abstinence is needed), and by telephone at the last day pre-quit, quit date, 1 week, 2 weeks, 4 weeks, 3 months (if biochemical verification of abstinence is not needed), 6 months (if biochemical verification of abstinence is not needed) and 1 year after the quit date.

Specific Aim 2: To determine if the effect of cessation pharmacotherapy (combination Nicotine Replacement Therapy (NRT) vs. varenicline vs. placebo for 3 months) on abstinence varies significantly with genotype. We will examine the association between two genetic variants in the CHRNA5 gene and treatment on smoking cessation success (abstinence at end of treatment (ABST\_EOT)). We will test the main effects of pharmacotherapy and genotype, as well as the interaction between them. Secondary cessation outcomes include abstinence at 6 months and 1 year.

### **C2 Secondary Aim**

To study the effect of other genetic or environmental risk factors on smoking cessation in this population.

### **C3 Rationale for the Selection of Outcome Measures**

We will conduct a randomized controlled smoking cessation trial of 822 participants to examine the association between the genetic variants (CHRNA5), treatment, and cessation success (abstinence at end of treatment (ABST\_EOT)). We will evaluate secondary cessation outcomes (abstinence at 6 months and 1 year).

**Primary Outcome Measure:** 7-day point prevalence abstinence [Time Frame: Week 12]  
The definition of this measure requires: (a) no self-reported smoking (not even a puff of a cigarette) for at least the 7 days prior to the assessment, and (b) CO biochemical verification of abstinence.

**Secondary Outcome Measures:** Continuous Abstinence (11 weeks) [Time Frame: 12 weeks with the first 1 week initial grace period]

The definition of this measure requires: Not taking even 1 cigarette puff from target quit date to end of treatment with the first 1 week initial grace period.

**7-day point prevalence quit rate** [Time Frame: Week 24]

The definition of this measure requires: (a) no self-reported smoking (not even a puff of a cigarette) for at least the 7 days prior to the assessment, and (b) biochemical verification of abstinence.

Number of days to lapse and relapse [Time Frame: Assessed from the target quit day through 52 weeks.]

The number of days to lapse is defined as the number of days from the target quit date until the participant reports smoking (even a single puff). The number of days to relapse is defined as the number of days from the target quit day until the first of seven consecutive days of smoking.

Initial Cessation [Time Frame: Assessed for the first seven days after the target quit date.]  
Defined as at least 1 day of abstinence during the first 7 days after the target quit day.

Longitudinal models of abstinence outcomes across multiple time points [ Time Frame: 0-52 Weeks ]

The definition of this measure requires; no self-reported smoking (not even a puff of a cigarette) for at least 7 days prior to the assessment.

Longitudinal models of smoking quantity in cigarettes per day outcomes across multiple time points. [ Time Frame: 0-52 Weeks ]The definition of this measure requires self-reported cigarettes per day.

Medication adherence [ Time Frame: Pre-quit week to Week 12 ]Adherence is the proportion of expected medication (varenicline, patch, lozenge) taken as advised during pre-quit week to week 12

Side effects [ Time Frame: Pre-quit week to Week 12 ]

All reported side effects (occurring>4%) will be summarized and presented for the study. In addition, the investigators will further identify a pre-specified set of key side effects as being related to drug agonist effects (e.g., nausea, vomiting, racing heart, headache, and sleep disturbance). These will be analyzed as rate of occurrence during the period of medication use.

Withdrawal [ Time Frame: Pre-quit week to Week 4 ]

Withdrawal severity is assessed by Wisconsin Smoking Withdrawal Scale (WSWS) overall withdrawal scores, craving, and negative affect scores.

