### **2.d Randomization Method and Blinding**

The participants will be randomized with the ratio 1:1:1 to the treatment arm of combination NRT (nicotine patch and lozenge) plus smoking cessation counseling, or the treatment arm of varenicline plus smoking cessation counseling, or the treatment arm of placebo (patch and lozenge or pill) plus smoking cessation counseling.

Participants will be randomly assigned to 1) combination NRT plus counseling, 2) varenicline plus counseling, or 3) placebo plus counseling. SAS Version 9 statistical software will be used to generate the random assignment table stratified by CHRNA5 genotype rs16969968. The group assignment and genotype will be coded to ensure that the double blind is maintained, and the interface will prevent staff from having access to the participant's assignment and genotype until after the baseline and post treatment assessments have been completed.

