### **2.e Risks and Benefits**

Risks associated with this research are judged to be minimal.

Smoking withdrawal is associated with a number of unpleasant symptoms such as sleep disturbance, hunger, craving, and negative mood. Most smokers have tried to quit in the past and are familiar with these phenomena.

With respect to the pharmacotherapy, participants will be made aware of the common side effects before they consent to participate in the study. It should be noted that the nicotine patch and lozenge are available over the counter. The nicotine patch has very few side effects, but participants may have a local skin reaction, and rarely, individuals may have a more systematic

---

allergic reaction. The most common side-effects associated with the nicotine patch are diarrhea, indigestion, nausea and vomiting, dry mouth, muscle and joint pain, sleeplessness, and abnormal dreams. Side effects associated with wearing an adhesive patch include skin rash, redness, and itching or irritation of the skin. The most likely side effects associated with the nicotine lozenge are heart burn, hiccup, nausea, upper respiratory track infection, coughing, and sore throat. In most cases, these side effects have been mild to moderate in intensity and go away once the patch is removed. Although most smokers have tolerance to nicotine, symptoms of acute nicotine toxicity (nausea and vomiting) are possible.

Varenicline is approved by the FDA for smoking cessation and is medically safe for most smokers except for individuals with severe (end stage) kidney failure or hypersensitivity to varenicline. In addition, although no causal relationship has been established, current labeling for varenicline (FDA, 2011) recommends monitoring for serious neuropsychiatric symptoms including changes in behavior, agitation, depressed mood, suicidal ideation, and suicidal behavior. Varenicline labeling also notes that some individuals with pre-existing psychiatric conditions may experience worsening of their conditions. Preliminary data from the University of Wisconsin Center for Tobacco Research and Intervention (UW-CTRI) smoking cessation trials showed comparable rates of discontinuation and adverse events due to NRT and varenicline. The low rate of serious adverse events is consistent with recent data on the safety of varenicline.

Blood draw may result in bruising, and very rarely, infection at the site of needle stick.

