Study participants will be closely monitored in accordance with current FDA recommendations as well as the consensus recommendations of the 2008 Guideline Panel which provides additional detailed instructions for clinicians regarding all FDA approved smoking cessation medications. We will follow the patient instruction and adverse events monitoring procedures used in the University of Wisconsin Center for Tobacco Research and Intervention (UW-CTRI). Patient education about possible side effects, access to a medication hotline, and ongoing monitoring will be consistent with FDA recommendations, clinical practice guidelines, and procedures successfully used in prior and ongoing UW-CTRI research using varenicline and combination NRT. This protocol is consistent with the 2010 FDA warning and recommendations for monitoring requirements regarding the black box warning of psychiatric risk for varenicline. In addition, we will make appropriate changes in study procedures if the FDA issues updates on varenicline.

All medical information and data from the interviews will be kept in a locked file cabinet in a locked office and identified by a code number. The master list of subject names will be kept in a separate locked file cabinet in a separate locked office by the Principal Investigator. Computerized research data are identified only by subject identification numbers and codes, and confidential data files are password protected. Written records of counseling sessions and audio recordings of sessions will be kept in a locked cabinet and will be destroyed within one year of the termination of the project. Audio recordings will be obtained if authorized by the participant. Only authorized individuals will be permitted to review these records. We have followed these procedures in the past without any breeches of confidentiality, and we feel certain that we will be able to maintain the same level of security for this project.

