#### **4.a Safety and Compliance Monitoring**

This study has a Data Safety and Monitoring Plan (DSMP), and a Data and Safety Monitoring Board (DSMB).

The Individual Patient Safety Committee (IPSC) will include the study's key personnel: [name]., M.P.H., Sc.D., a psychiatrist; [name]., a psychologist; [name]., a psychiatrist; The IPSC will review monthly reports on all participants. The IPSC will be blinded to the patient's group assignment.

In addition, we have a Data Safety and Monitoring Board (DSMB). The DSMB specifies overall monitoring that will be conducted by the principal investigator, including timely reporting of AEs and SAEs. Every 6 months, the DSMB will convene to review the overall safety data, and data on safety summarized by treatment condition. As per NIH guidelines, the objective of these reviews will be to determine whether continued conduct of the trial poses any undue risk for participants.

The DSMB will include 1) a board-certified psychiatrist, [name], 2) a cardiologist, [name], 3) an internist specialize in critical care and pulmonary health, [name], 4) an internist with expertise in stroke prevention and personalized antithrombotic therapy, [name], and 5) a statistician with expertise in research methodology, especially multicenter clinical trials and analysis of administrative data sets, [name]. All five have extensive experience with clinical trials. The DSMB will be blinded through the trial and convene every 6 months to compare the groups with respect to adverse events, dropouts, withdrawals, suicidality, and other problems as well as efficacy. They will make a recommendation at each meeting regarding whether to continue or discontinue the trial, the decision will be adjudicated by the Washington University Human Studies Committee.

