## **F Statistical Plan**

### ***F1 Sample Size Determination and Power***

We will recruit 822 subjects for this study to examine whether genotypes predict the efficacy and side effects of cessation medications. The sample size is based on the statistical power calculation based on current research findings. Based on published finding of effect size (OR=3.1), we will have power of 0.84 to detect a hypothesized interaction effect size of 2.0 with the study design (2 sided  $\alpha=0.05$ , abstinence rate 20% in the placebo group).

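### The 4% cut-off and the agonist-only key set in C3 could leave the neuropsychiatric events flagged for varenicline out of the reported side-effect results

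*Combined protocol and SAP*

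**What the plan says.** Section C3 lists side effects as a secondary outcome, from the pre-quit week to week 12. The reporting rule has two parts.

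- A frequency rule: "All reported side effects (occurring>4%) will be summarized and presented for the study". The base of the percentage (whole trial, each arm, or any arm) is not given.
- A key set, described as "a pre-specified set of key side effects as being related to drug agonist effects (e.g., nausea, vomiting, racing heart, headache, and sleep disturbance". For this set C3 adds: "These will be analyzed as rate of occurrence during the period of medication use". That sentence does not mention comparison by arm.

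Section 2.e singles out a different class of event for varenicline. It notes that the labeling "recommends monitoring for serious neuropsychiatric symptoms including changes in behavior, agitation, depressed mood, suicidal ideation, and suicidal behavior", and it says the protocol is consistent with "monitoring requirements regarding the black box warning of psychiatric risk for varenicline".

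Section F1 puts side effects within the trial's purpose: "We will recruit 822 subjects for this study to examine whether genotypes predict the efficacy and side effects of cessation medications".

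On monitoring, section 4.a (repeated in H1) has the DSMB meet every 6 months to "compare the groups with respect to adverse events, dropouts, withdrawals, suicidality, and other problems as well as efficacy". Sections 4.b, 4.f and H1 require each serious event to be queried and reported, with no frequency threshold. Sections F3 and F4 refer to Appendix K10 for analysis detail; the text available for this review contains only the heading of K10.

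**The concern.** The events that the protocol itself identifies as the psychiatric risk of one active arm are not assured a place in the side-effect outcome. The key set is introduced with examples, so it is not a closed list. Its defining criterion is agonism, however, and of the examples only sleep disturbance comes near the neuropsychiatric class. Agitation, depressed mood, change in behavior and suicidality therefore fall under the general rule, which presents them only if they pass 4%.

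A frequency filter suits a table of common, mild effects. It suits uncommon events of high consequence poorly, because a difference between arms can sit entirely below the line. What is at stake is whether readers of the results can weigh varenicline's benefit against the risk that 2.e describes.

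**Working it through.** The documents derive no figure for the 4% cut-off, so there is none to reproduce. The check is how large a difference between arms can stay at or below the cut-off under each reading of the denominator.

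**Inputs.** Total 822 (F1). Allocation: "The participants will be randomized with the ratio 1:1:1 to the treatment arm of combination NRT", and likewise to varenicline and to placebo (2.d). Cut-off: more than 4% (C3). Per arm: 822 / 3 = 274, with placebo taken as one arm.

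**Test used for illustration.** Two-sided Fisher exact test, varenicline versus placebo, 274 in each, no adjustment for multiplicity.

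1. *Cut-off applied within an arm.* 0.04 × 274 = 10.96, so an event in up to 10 participants of an arm (10/274 = 3.65%) need not be presented.

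| Varenicline | Placebo | p |
|---|---|---|
| 10 (3.65%) | 0 | 0.002 |
| 10 (3.65%) | 2 (0.73%) | 0.037 |
| 10 (3.65%) | 3 (1.09%) | 0.088 |
| 6 (2.19%) | 0 | 0.030 |

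2. *Cut-off applied to the whole trial.* 0.04 × 822 = 32.88, so up to 32 participants with the event (32/822 = 3.89%) need not be presented. Giving cNRT and placebo equal counts and using all 32:

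| Varenicline | cNRT | Placebo | p, varenicline vs placebo |
|---|---|---|---|
| 20 (7.30%) | 6 | 6 (2.19%) | 0.008 |
| 18 (6.57%) | 7 | 7 (2.55%) | 0.039 |
| 16 (5.84%) | 8 | 8 (2.92%) | 0.14 |

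A split of 24 versus 8 gives p = 0.0055, but it uses all 32 events and so requires none in the third arm. The 20/6/6 split is the fairer illustration.

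3. *What the extra table would and would not do.* Take assumed true rates of 1% and 3.5%, with a pooled variance under the null:
   - mean rate (0.01 + 0.035)/2 = 0.0225
   - null SE = √(2 × 0.0225 × 0.9775 / 274) = 0.01267
   - alternative SE = √((0.01 × 0.99 + 0.035 × 0.965) / 274) = 0.01263
   - power = Φ((0.025 − 1.96 × 0.01267) / 0.01263) ≈ 0.51

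   The table would serve disclosure. It would not be a well-powered test.

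4. *Is the gap filled elsewhere?* Of the places that touch on the matter, 4.a and H1 provide DSMB comparisons; 4.b, 4.f and H1 provide individual reports to the IRB, the FDA and the manufacturer. F5 says groups will be compared on side effects, but within the handling of discontinuation and missing data and without naming events. C3 also lists WSWS negative affect to week 4, a withdrawal score that does not count events. None commits to a by-arm table of the 2.e events in the results.

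**The case against.** The strongest reply is that these events are far from unwatched, and most of it stands.

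- *A reader might infer that such differences would never be shown.* The documents do not support that. The DSMB compares the groups on adverse events and suicidality every 6 months, with safety data summarized by treatment condition. What remains is narrower: those comparisons serve the decision to continue or stop, and nothing places them in the trial's results.
- *A reader might infer that the filter removes rare serious events.* It does not remove them from safety reporting. Sections 4.b, 4.f and H1 require serious events to be reported whatever their frequency, and 4.g has adverse events recorded and reported for the full year. The C3 rule governs the side-effect outcome only. Even so, individual reports are not a by-arm table, and agitation or depressed mood that is not serious need not follow the serious-event route.
- *A reader might infer that these events will probably fall under 4%.* The documents give no expected rate. Section 2.e lists negative mood among withdrawal symptoms, so depressed mood could exceed 4% and be shown. The point rests only on the absence of a commitment when an event does not exceed it.
- *The examples are at the edge.* This is fair: 10 versus 3 already gives p = 0.088. They show what the rule permits and predict nothing.
- *The F1 purpose adds little.* This is also fair. With 10 or fewer events in an arm spread over three genotype groups, no genotype question about them could be answered, tabulated or not. The case rests on comparison by arm.
- *Appendix K10 may already specify full adverse-event tables.* That cannot be determined from the available text. If it does, C3 only needs to be brought into line with it.

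**Conclusion.** The point holds in a limited form. Followed as written, C3 allows the neuropsychiatric events flagged in 2.e to differ between arms and not appear in the reported side-effect results whenever they fall at or below 4%. The unstated denominator matters. Under the per-arm reading up to 10 of 274 in an arm can go unpresented; under the pooled reading up to 32 of 822 can, and these may be concentrated in one arm.

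This rests on full recruitment with equal arms, on placebo being treated as a single arm, on reading the key set by its stated criterion, and on K10 not already containing the table. The event splits are assumptions and the p-values are nominal. The point concerns reporting of results. It is not a finding that safety monitoring is deficient. It deserves correction because the protocol itself names the risk and the remedy is small.

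**What to change.** In C3:

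1. State the denominator of the 4% cut-off, for example participants in any one arm who were dispensed medication.
2. Restrict the cut-off to the table of common non-serious side effects.
3. Add a sentence such as: *All serious adverse events, all neuropsychiatric events named in section 2.e, and all events leading to dose change or discontinuation will be tabulated by treatment arm regardless of frequency.*

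If K10 already specifies such a table, amend C3 to refer to it. The cost is a few lines of text and one extra table. The adverse-event screener is already administered at follow-up (E2, E4), and reasons for discontinuation are already classified (F5). No visit, assessment or clinical rule changes.
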